Study Title: Effects of combined exercise training and Ketone ester on muscle strength and cardiovascular response in Parkinson's disease

PI: [name]

Study ID: HUM00232413

NCT#: NCT05948956

Protocol Version IRB Approval Date: 12/12/2024

Effects of combined exercise training and ketogenic diet on muscle strength and cardiovascular response on Parkinson's disease

Background: Most of the research emphasis in Parkinson's disease has been on the basal ganglia and dopamine. This research paradigm has led to the successful introduction of dopaminergic drugs in clinical practice. Although L-DOPA remains the mainstay of PD management to date, this drug fails to prevent disease progression. In contrast, accumulating evidence has shown that exercise may be the only therapy with disease-modifying effects in PD. The ability to exercise optimally declines with disease progression due to systemic frailty and sarcopenia in advancing PD. In other words, those persons with PD who need exercise the most may be the least able to reap its benefits. Previous work on ketone supplementation has established an improvement in endurance cycling performance in persons with Parkinson disease (PwPD) (Norwitz et al., 2020) and elite athletes (Cox et al., 2016).

Critical Knowledge Gap: Although exercise is known to have effective disease-modifying effects on PD progression, there are no standard therapies to improve muscle bioenergetics so that biological effects of exercise can be better exploited over time in people with PD. A prior study showed that one-time consumption of a ketone ester supplement boosted endurance exercise in PwPD. Effects of ketone supplementation on cumulative exercise sessions, and benefits to strength versus cardiovascular endurance remain unknown.

Problem to be solved: A critical but unmet need in exercise management of PD is the lack of an effective therapy to improve muscle bioenergetics during exercise so that biological effects of exercise can be better exploited in people with PD over time. Repeated dietary supplementation with a ketone ester presents a promising, incompletely understood potential intervention.

Specific Aim: To explore the effect of ketone ester supplementation on aerobic exercise tolerance in persons with Parkinson's disease.

Hypothesis: Ketone ester will help improve exercise performance on endurance cycling at 80 rpm at a personalized fixed-wattage, and improve performance on the quadriceps maximal strength test when compared to exercise alone.

Background

Ketone supplementation in neurodegeneration and exercise:

Ketone ester supplementation, and the ketogenic diet (consisting of preferential intake of predominant medium and long-chain fatty acids and minimization of carbohydrates) have become a subject of recent research in metabolic and neurodegenerative disorders. Preliminary positive findings have been reported mainly from short-duration studies. Both the ketone supplementation and the ketogenic diet are meant to induce a state of ketosis, characterized by elevated levels of ketone bodies in the blood.

Ketones levels in blood are naturally elevated during a fasting state, or during a low glycemic state which may brought on by performing a prolonged bout of exercise. The exogenous C8 ketone di-ester used in this study is a naturally occurring molecule in the body and is converted to ketone bodies by the liver by the same mechanisms as endogenously produced ketone esters.

KE supplementation in elite athletes has previously been shown to enhance endurance exercise performance in elite cycling endurance (Cox et al., 2016). In addition, a proof of principle study from Oxford demonstrated that one-time KE supplementation improved aerobic exercise endurance in participants with PD (Norwitz et al., 2020) on a maximal endurance cycling test.

Exercise interventions and Parkinson's disease:

There are currently no disease-modifying drug therapies for PD. Standard treatment involves dopamine replacement with levodopa, a medication that has a temporary window of efficacy, can induce dyskinesia, and does not address the non-motor symptoms of PD (Hinnel and Ray, 2009). Moderate to high-intensity exercise may be the only therapy with disease-modifying effects in PD. A comprehensive review of PubMed literature from the Mayo clinic concluded that there is compelling evidence of midlife cardiovascular exercise slowing the disease progression of PD (Ahlskog., 2018). Research in animal models has shown that exercise has neuroprotective effects against dopaminergic toxins such as 6-OHDA and MPTP (Tajiri et al., 2010). Retrospective study of the interaction of exercise and incidence of Parkinson's (Chen et al., 2005; Thacket et al., 2008; Xu et al., 2010) demonstrates that vigorous exercise in midlife reduces the risk of developing PD. When assessing exercise history, engaging in moderate to high-intensity exercise was associated with a 38% reduced risk of developing PD.

In addition, cycling is known to be an accessible and beneficial exercise mode even for PD patients who exhibit freezing of gate (FOG), who may not be able to exercise effectively through walking or running. FOG is associated with abnormal beta-band oscillations in the cortico-basal ganglia loop during walking, and these abnormal oscillations are reported to be weaker and briefer upon initiation of cycling movements. This is suggested to be due to the continuous nature of cycling, and the lower amount of proprioception required to maintain balance as compared to walking (Licen et al., 2022). Previous interventional exercise studies have also emphasized the cadence of cycling as a critical factor for therapeutic benefit to PWPD. Cycling at 80 RPM conferred benefits to motor symptoms of PD on the UPDRS that last for at least a month, and such improvements were not seen at lower cycling cadences (Ridgel et al., 2009, 2015, 2019). No significant reduction was shown for participation in light physical exercise. In addition, the Study in Parkinson's Disease of Exercise (SPARX) reported that high-intensity treadmill exercise but not moderate-intensity exercise, prevented progression of motor symptoms of PD over 6-months (Schenkman et al., 2018). These data suggest that vigorous exercise is disease-modifying in PD.

Overall strategy

General Overview: Sixteen patients with Parkinson's disease (PD) will be recruited to participate in this exploratory clinical study with a randomized, placebo-controlled, double-blind design. Patients will be randomized into one of two groups: (1) Group A (experimental): consuming ketone ester (KE) beverage before each of 12 1-hour sessions of aerobic exercise, or (2) Group B (control): consuming placebo electrolyte (EL) beverage before each of 12 1-hour sessions of aerobic exercise. Participants will have 3 testing visits and 12 intervention visits to the laboratory over the course of 4-6 weeks. Patients will undergo physical, cognitive, and metabolic testing before and after the endurance cycling intervention. Prior to exercise testing participants will be cleared for exercise by a resting twelve-lead electrocardiogram and Physical Activity Readiness Questionnaire. Primary Outcomes will consist of the time of 80 rpm endurance test, and VO2 testing during exercise and rest (Cosmed Quark). Additional optional measures of isometric and isokinetic quadriceps muscle strength (Biomed 4 dynamometer) and/or hand grip strength may be collected. Blood levels of glucose, β -HB, and lactate will be sampled and measured throughout each interventional day by fingerstick- up to 3 samples will be taken at each visit. Blood lactate will be measured using a The Edge™ device, and blood glucose and β -HB will be measured using a Keto-Mojo™ device. Participants will be asked to wear a continuous glucose monitor (CGM) during the study. An MRI scan of the brain will be performed pre and post intervention to study network connectivity changes as an exploratory outcome.

Participants and Screening

Human Subjects

Description of subject populations:

PD (net n=24) Diagnosis of PD in PD participants (M/F, age 45 years and over) will be based on the United Kingdom Parkinson's Disease Society Brain Bank Diagnostic Research Criteria (patients with clinically significant dementia will be excluded; Hoehn & Yahr Stages 1-2.5 included)

Exclusion criteria:

1. Any recent changes in EKG, history of myocardial infarction or other cardiac event or other cardiac contraindications to exercise
2. Inability to use a step, stand, walk, or use a stationary cycle ergometer;
3. History of symptoms in exercise that preclude safe and comfortable participation, such as dizziness and lightheadedness, orthostasis, severe symptomatic leg or back musculoskeletal pain, painful neuropathy, significant ankle edema or medication side effects;
4. History of symptomatic cardiovascular or pulmonary disease interfering with exercise;
5. History of active rheumatoid arthritis;
6. History of uncontrolled chronic pain syndrome;
7. Any other history of medical or psychiatric comorbidity precluding safe participation in the project;
8. Poorly controlled diabetes
9. Pregnancy or breastfeeding
10. Clinically significant dementia
11. Any contraindications to MRI (metal implants, severe claustrophobia, inability to lie still for 1 hour, etc.) The MRI portion of the study is optional, so participation in the remainder of the study can occur for individuals with contraindications to MRI.

Study timeline: This study, to be conducted over a 2-year period, will include a net total of n=24 subjects (22 participants + 2 for 10% attrition of drop out).

Subject Recruitment: Prior to any research procedures, written informed consent will be obtained from each subject followed by initial study eligibility screening. PwPD subjects will be recruited from the University of Michigan Functional Neuroimaging, Cognitive & Mobility Laboratory subjects list who have consented to be contacted for new studies.

Study design: Phase 1B randomized controlled clinical trial.

Baseline Testing

After obtaining informed consent and screening for study eligibility, study participants will undergo the baseline clinical assessment. The exploratory motor components of the test battery will be performed in the dopaminergic medication 'off' state in the morning after overnight withholding of their dopaminergic medications. Participants will complete the MDS-UPDRS, MINI-BEST & APDM, Biodex strength assessment

followed by the baseline aerobic test, the 80 rpm endurance test, and the anaerobic threshold test. Following the motor testing, participants will take their dopaminergic medication and complete the exploratory neuropsychological evaluations and questionnaires. The exploratory neuropsychological assessments include Judgement of Line Orientation test (JLO), Parkinson's Disease Cognitive Rating Scale (PD-CRS), Parkinson's Disease Cognitive Function Rating Scale (PD-CFRS), California Verbal Learning Test II (CVLT-II), Delis-Kaplan Executive Function System (D-KEFS), Wechsler Adult Intelligence Scale III (WAIS-III), and Wechsler Memory Scale (WMS-III). The questionnaires include the Parkinson's Disease Questionnaire (PDQ-39), Fatigue Severity Scale (FSS), Epworth Sleepiness Scale, Physical Activity Questionnaire, and the Beck Depression Inventory II (BDI-II).

Baseline Aerobic Test

To determine intensity for the training intervention, participants will engage in a baseline aerobic test (Norwitz et al., 2022). Participants will come in fasted and following overnight withdrawal of dopaminergic medication (levodopa and dopamine agonists), in an “off” state. After being cleared for exercise by a resting 12-lead electrocardiogram, blood glucose test ($>70\text{mg/dL}$), and physical activity readiness questionnaire, participants will be instructed to cycle on a Keiser cycle ergometer at a controlled cadence.

After familiarization with the cycle ergometers, description and explanation of the procedures and adjustments related to body position as well (seat height, seat distance, and handlebar on each cycle ergometer), the test will begin with standardized warm-up at cadence of 80 rpm at 50 watts for 4 minutes. Thereafter, wattage will increase by 10 Watts every 2 min until the participant voluntarily ends the test or is unable to sustain a cadence of >70 rpm at the wattage interval. 30 seconds before the end of each stage participants will be asked to rate their exertion on the Borg RPE scale (6-20). Resting heart rates, heart rates taken at the end of each stage of the baseline test, and approximated maximum heart rate ($220 - \text{age}$) will be used to create a linear regression of wattage as a function of heart rate. Each participant's fixed-Watt value for subsequent tests will be set at 55% of their projected wattage at a maximum heart rate. In order to standardize test length, participants exhibiting lower physical capacity will begin at 25 watts for the baseline test, or cycle at 75% of projected wattage at maximum heart rate on the endurance test. The Keiser™ M3 cycle ergometer, the wattage is calculated as the product of speed (rpm) for the gear (from 1 to 24), considering the time required (in minutes) for its 16.8kg wheel to travel one meter, and is presented on the display (Viega et al., 2020).

80 rpm Endurance Test

The endurance test will be conducted on the same cycle ergometer as the baseline test and begin with the same 4-minute warmup at 50 watts. Thereafter the participants will cycle at their personalized fixed wattage at 80 rpm until failure, defined as the point at which the participant could not sustain a cadence of >70 rpm for a cumulative total of 20 s, or until voluntarily choosing to end the test (Norwitz et al., 2022). Participants will be encouraged verbally throughout the test.

One-Minute Anaerobic Threshold Test

After the 80 rpm endurance exercise test, participants will rest their heart rates return to near baseline and they self-report they feel fully recovered (~5 min rest). Participants will then engage in a 1-min anaerobic threshold test. Participants will be instructed to cycle at as high a cadence as possible at the ergometer resistance that achieves their personalized target wattage (calculated from baseline test) when cycling at 80 rpm (Norwitz et al., 2022). Within 60s, immediate post-exercise, β -HB, glucose, and lactate levels will then be measured.

Biodex Strength Test

Participants will sit (~85° hip flexion) on an ergometer (Biodex System 4). The upper body will be stabilized with straps across the thorax and abdomen. Knee joint axis of rotation will be aligned with the measurement axis of the system. The leg being tested will be strapped around the mid-thigh. The knee angle will be placed at 90° to cancel the effect of gravity on the test. Participants will be instructed to perform maximal effort during a static knee extension and to limit countermovement. At least three maximal voluntary contractions will be recorded. A fourth and possibly fifth trial will be performed if the value reached during the last trial is higher than the preceding ones, or if the difference between trials was greater than 10%. Participants will be encouraged verbally throughout the test. Primary outcome will be the mean torque value for each leg. Biodex testing for isometric strength is established as the gold standard in the field and highly reliable (Feiring et al., 1990). Protocol for Biodex isometric testing on knee extensors taken from prior studies at University of Manitoba (Ogborn et all., 2021)

Magnetic resonance imaging (MRI)

The exploratory MRI scan will be performed on a 3 Tesla Philips Achieva system (Philips, Best, The Netherlands). A 3D inversion recovery-prepared turbo-field-echo was performed in the sagittal plane using TR/TE/TI=9.8/4.6/1041ms; turbo factor=200; single average; FOV=240x200x160mm; acquired Matrix = 240x200x160 slices and reconstructed to 1mm isotropic resolution. Resting-state fMRI scans will be acquired using a 32-channel head coil and multi-band sequence (32), with nominal parameters: (TR/TE/FA = 720/34/52, 2mm isotropic resolution, 72 slices). Data are collected with eyes fixated on a cross for 10 minutes (33). Pre-processing follows our standard pipeline that includes physiologic noise reduction and thorough motion correction (34, 35). Graph theory analysis will be used to identify the most highly connected nodes following published methods. Briefly, ROIs will be represented as nodes and pairwise correlations, based upon the mean time series for each ROI, will serve as weights over corresponding edges, thresholded by FDR correction, $p<0.05$ (34, 35). Change from baseline will serve as the primary measure of interest in this optional assessment.

Intervention

Cycling Intervention

After the baseline cycling test day, the participants will come into the lab to complete twelve 1-hour sessions of cycling on the ergometer, 1-hour exercise per visit across a 4-6-week period. On each intervention day, study participants will arrive fasted and 1-hour prior to exercise they will take their dopaminergic medication followed by ketone ester or electrolyte placebo. Physical activity readiness questionnaire and heart rate monitoring will be done before the beginning of each session. Before each exercise session, participants will have their blood glucose measured and assessed to determine if it is within the normal range. Participants displaying hypoglycemia (blood glucose <70mg/dL) will discontinue

exercise for that session and reschedule. Participants displaying hypoglycemia a second time will discontinue the study and be referred to their primary care physician.

[figure not shown]
For each session, participants will complete a 10 min warm up followed by 8 intervals consisting of 3 min “fast” cycling at 80-90 PM followed by 2 min of “slow” cycling at ≤ 60 rpm, followed by a 10-minute cooldown. Target HR for “fast” intervals will be 75% estimated max heart rate, measured at the peak HR typically shortly (within ~10s) after each interval. Ergometer resistance will be adjusted throughout the session to allow the participant to consistently reach their target HR. This protocol is based on a study in which PD participants followed these training parameters 3x/wk for 8 weeks and exhibited improved neurological and motor symptoms of PD compared to normal controls (Mariusiak et al, 2019).

To assess the impact of ketone supplementation alone on patients’ exercise performance, participants will come into the lab in an “off” (abstaining from dopaminergic medication) and overnight fasted (>8hr) state, in the same fashion as the baseline testing procedure. After arrival, the participant will take their medication and at 1-hr prior to exercise testing participants will have β -HB, glucose, and lactate levels measured by fingerstick. A new lancet will be used to draw blood from either the index or middle finger and the first drop of blood will be discarded prior to measurements. Immediately thereafter, the participants will receive either the KE drink or the EL drink. 1-hr after receiving the study drink, participants will again have β -HB, glucose, and lactate levels measured before beginning the training. These blood values will be measured again immediately following the exercise session.

Drink Preparation and Randomization

The two drink preparations that will be used in this study are a ketone ester plus electrolyte drink (KE), consisting of 2 scoops (=25 g C8-KE) of Quitone Pro-Ketone Powder and electrolyte solution diluted in water, and an electrolyte only drink (EL) consisting of electrolyte solution diluted in the same amount of water. Drinks will be prepared in a room separate from participants and administered in an opaque container. As this is a randomized study, the order in which the drinks are presented to the participants will be determined by a random number generator, with even numbered participants receiving the KE drink and odd numbered participants receiving EL drink. One study team member will be responsible for mixing all the beverages administered in the study, will maintain the a log indicating which participants were in the placebo arm or the treatment arm, and this team member will not participate in any assessments or data collection in the study. The other study team members will not be unblinded until the conclusion of the entire study.

Study outline:

Assessment Schedule:

	Baseline: Visit 1	Exercise Intervention Visits 2-6, 9- 14	2 nd Assessment: Visit 7	Post- Testing: Visit 15
Total Time	6 hours	2 hours	6 hours	6 hours
Informed Consent	✓			
Demographic Information	✓			
Inclusion/Exclusion Criteria	✓			
Clinical, Balance & Neurological Assessment ⁽¹⁾	✓		✓	✓
Resting Electrocardiogram	✓			
Blood measurements		✓		
Ketone Ester Supplement or placebo		✓		
BiDex Strength Assessment	✓		✓	✓
Baseline Aerobic Test ⁽¹⁾	✓			
Cycling Intervention		✓		
80 RPM Endurance Test ⁽¹⁾	✓		✓	✓
One-Minute Anaerobic Threshold Test ⁽¹⁾	✓		✓	✓
*MDS-UPDRS I &II	✓		✓	✓
*MDS-UPDRS III ⁽¹⁾	✓		✓	✓
*Mini-BESTest ⁽¹⁾	✓		✓	✓
APDM Mobility assessments ⁽¹⁾	✓		✓	✓
*PDQ-39	✓		✓	✓
Activity questionnaire	✓		✓	✓
*MoCA	✓		✓	✓
*PD-CRS ⁽²⁾	✓		✓	✓
*PD-CFRS ⁽²⁾	✓		✓	✓
*JOLO ⁽²⁾	✓		✓	✓
*CVLT-II ⁽²⁾	✓		✓	✓
*D-KEFS ⁽²⁾	✓		✓	✓

*WAIS-III ⁽²⁾	✓		✓	✓
*WMS-III ⁽²⁾	✓		✓	✓
*Epworth Sleepiness Scale	✓		✓	✓
*FSS	✓		✓	✓
BDI-II	✓		✓	✓
Adverse event assessment	✓	✓	✓	✓
DEXA	✓		✓	✓
*MRI	✓		✓	✓
Urine pregnancy test in women of childbearing potential	(Within 48 hours of the dexa scan)		(Within 48 hours of the dexa scan)	(Within 48 hours of the dexa scan)

(1) Performed in dopaminergic “off” state- unless otherwise noted in this table, all assessments performed in “on” state (taking dopaminergic medication); * Exploratory measure.

Statistical analysis:

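### The protocol gives two incompatible sample sizes, 16 and 24, for the same randomised cohort

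*Combined protocol and SAP*

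**What the plan says.** Three places in the combined protocol and SAP give a sample size.

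- **Overall strategy, General Overview:** the target is given as "Sixteen patients with Parkinson's disease (PD) will be recruited". The next sentence begins "Patients will be randomized into one of two groups", so the 16 are the whole two-arm cohort.
- **Participants and Screening, Human Subjects:** "PD (net n=24) Diagnosis of PD in PD participants".
- **Study timeline:** the study "will include a net total of n=24 subjects", split into "22 participants + 2 for 10% attrition of drop out".

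Subject Recruitment adds that "written informed consent will be obtained from each subject followed by initial study eligibility screening". The number consented and the number randomised can therefore differ.

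The Statistical analysis section specifies two-tailed t-tests on change. It gives no sample size, effect size, standard deviation or power that would show which figure is current.

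**The concern.** The protocol describes one disease population and one randomised study, so 16 and 24 cannot both be its enrolment target. All three statements are current protocol text, and none is ranked above another.

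The target is the only thing that fixes when enrolment ends. With two targets, stopping at either could be defended as planned. In a small trial without a stated sample-size justification, a fixed target guards against a stopping point chosen after data have accrued. Blinding of everyone except the person who mixes the drinks lessens that risk, but it does not tell anyone when to stop. The choice also changes the precision of the primary comparison.

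**Working it through.** **Inputs from the document:** 16 (General Overview); 24 (Human Subjects and Study timeline); 22 + 2 and 10% attrition (Study timeline); two arms (General Overview); two-tailed t-test (Statistical analysis).

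**Assumed, not stated:** equal arms and a 95% confidence level. The even/odd rule in Drink Preparation and Randomization suggests roughly 1:1 but gives no ratio.

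**1. Reproduce the plan's 24.** 22 / (1 − 0.10) = 24.4, and 22 × 1.10 = 24.2. In reverse, 24 × 0.90 = 21.6, or about 22. The allowance of 2 is 2/22 = 9.1% or 2/24 = 8.3%. The step from 22 to 24 is therefore consistent with about 10%, allowing for rounding.

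**2. Try to connect 16 to the other figures.**

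- 16 as completers out of 24: dropout = 1 − 16/24 = 33.3%, against the stated 10%.
- 16 as completers, inflated for 10% attrition: 16/0.9 = 17.8, so 18, not 22 or 24.
- 16 per arm: the total would be 32, which appears nowhere.
- 16 as the optional MRI subset: the sentence concerns the whole randomised study.
- 24 as the number screened: it is built from a dropout allowance, not a screen-failure allowance.

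None of these works.

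**3. Size of the gap.** 24/16 = 1.5, so the larger target is 50% above the smaller.

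**4. Effect on precision.** In units of the standard deviation of the change score, the half-width of the 95% confidence interval for the between-group difference is t(0.975, n1 + n2 − 2) × √(1/n1 + 1/n2).

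| Per arm | Calculation | Half-width (SD) |
|---|---|---|
| 7 | 2.179 × √(2/7) | 1.165 |
| 8 | 2.145 × √(2/8) | 1.072 |
| 11 | 2.086 × √(2/11) | 0.889 |
| 12 | 2.074 × √(2/12) | 0.847 |

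Ratios of the smaller target to the larger:

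- Enrolled against enrolled, 8 v 12 per arm: 1.0724/0.8467 = 1.27.
- Both after 10% attrition, unrounded, 7.2 v 10.8 per arm: 1.1442/0.8988 = 1.27. Rounded to 7 v 11: 1.1646/0.8895 = 1.31.
- If 16 meant completers, 8 v 11 per arm: 1.0724/0.8895 = 1.21.

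Moderately unequal arms make little difference. For example, 6:10 v 9:15 gives 1.1076/0.8744 = 1.27.

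**The case against.** The contradiction itself has no good answer, but several points bear on how far it should be pressed.

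- **The precision range is partly artificial.** The 21% needs 16 to mean completers, although the overview says recruited, and the 31% comes from rounding 7.2 down and 10.8 up. This is fair: about 27% is the like-for-like figure, and the rest is a sensitivity range.
- **The documents do not show that 24 is current.** It appears twice and is the only figure with any build-up, but the 22 beneath it is not derived from anything. The overview is not obviously out of date either: its 12 sessions match the Cycling Intervention section. This also stands. 24 is at most the likelier intent, and only the sponsor can settle it.
- **Reading 22 as expected completers is an inference.** The text calls them participants and adds 2 for attrition. The inference is reasonable, but the protocol should say it outright.
- **The trial is exploratory, Phase 1B, with no power claim or stopping rule to breach.** This limits the severity, but it does not supply an enrolment target.
- **The word *net* attached to 24 is a minor label problem.** The figure includes the dropout allowance, but Study timeline spells out the split, so no number changes.

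**Conclusion.** The concern holds. The protocol sets enrolment at 16 in one place and at 24 in two others, for the same randomised cohort, and neither the stated attrition nor any other text reconciles them. That conclusion needs no assumptions.

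The effect on precision does rest on assumptions (equal arms, 95% level): about 27% wider at the smaller target, with a range of 21% to 31%. This is a definite error in a basic design figure and should be corrected. By itself it neither endangers participants nor invalidates the planned analysis.

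**What to change.** The sponsor should confirm one number and state which population it counts: consented, randomised or completing. General Overview, Human Subjects and Study timeline should then carry the same figure, give the target and the expected completers separately, and drop *net* from any figure that includes the dropout allowance.

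- **If 24 is confirmed:** change the overview to *twenty-four*, with the population named. Give Human Subjects as *n=24* with the same population. Have Study timeline say that about 22 of the 24 are expected to complete, allowing about 10% attrition.
- **If 16 is confirmed:** correct both 24s and the 22 + 2 statement. Say whether 16 are enrolled (16 × 0.9 = 14.4, about 14 completers) or 16 are to complete (16/0.9 = 17.8, about 18 enrolled).

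The cost is wording changes in up to three places once the number is confirmed.

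Optionally, the Statistical analysis section could say that enrolment ends at the confirmed number and give the expected precision. Assuming equal arms, the 95% half-width is about 0.89 SD with 22 analysed, 1.07 SD with 16 and 1.16 SD with 14. Because the stated primary comparison is made after 5 sessions, the number analysed then may exceed the number completing the study, so the text should name the time point. It should also present the figure as interval precision, not as a detectable difference. This would be new statistical content, and its one drawback is that it shows openly how imprecise the estimate will be.

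### No rule keeps post-drink β-HB readings, which are likely to indicate the arm, from the staff who run and encourage the endurance and anaerobic tests

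*Combined protocol and SAP*

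**What the plan says.** In the combined protocol and SAP, General Overview describes a "randomized, placebo-controlled, double-blind design". On outcomes it states: "Primary Outcomes will consist of the time of 80 rpm endurance test", together with VO2. Of the fingersticks for glucose, β-HB and lactate it says that "up to 3 samples will be taken at each visit", and it names one device for both glucose and β-HB.

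Drink Preparation and Randomization gives the safeguards: a separate preparation room, an opaque container, and a single team member who mixes every drink and keeps the log. Of that person it says "this team member will not participate in any assessments or data collection in the study". All other team members are to stay blinded until the study is over. The same section refers to a random number generator and ties even numbers to the ketone ester (KE) drink and odd numbers to the electrolyte (EL) drink.

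Cycling Intervention calls for β-HB before the drink, one hour after it, and right after exercise. The background section on ketone supplementation says that supplements and the ketogenic diet "are meant to induce a state of ketosis, characterized by elevated levels of ketone bodies in the blood".

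Under 80 rpm Endurance Test, the criterion for failure is "the point at which the participant could not sustain a cadence of >70 rpm for a cumulative total of 20 s". There is a second way for the test to finish, since the section also allows cycling to go on "or until voluntarily choosing to end the test". On the conduct of staff it states: "Participants will be encouraged verbally throughout the test". The one-minute anaerobic test that follows asks for maximal cadence.

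**The concern.** The safeguards conceal the drink but not the blood marker that the drink is meant to change. Staff who see a participant's β-HB before and after the drink, session after session, may work out the arm. If they then run that participant's endurance test, the strength of their encouragement could differ by arm. A participant who learns the values could also choose to stop sooner or later because of them. Baseline testing comes before any study drink, so such a difference would enter the change score directly, and the planned t-test on change would attribute it to the drink. The one-minute anaerobic test depends on effort in the same way and is named in the same comparison.

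**Working it through.** The plan states no figure for this point, so the check consists of setting the sections side by side and counting readings.

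**Who takes the readings**
1. The only team member who knows the arms is the drink mixer, who is excluded from data collection (Drink Preparation and Randomization).
2. β-HB must be measured after the drink (Cycling Intervention).
3. By elimination, the measurement falls to team members who are counted as blinded.
4. Supplementation is meant to raise blood ketones, and the comparator is electrolyte only. The change from pre- to post-drink β-HB is therefore likely to indicate the arm.
5. No section masks the value, limits access to it, or separates those who take it from those who run the endpoint tests. The Data & Safety Monitoring Plan speaks only of research staff who test, score and enter data, without dividing the roles.

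**How many readings**
- Samples per visit: at most 3 (General Overview).
- Pre-drink samples: 1 (Cycling Intervention).
- Post-drink readings per session: 3 − 1 = 2 at most.
- Before the comparison after 5 sessions (Statistical analysis): 2 × 5 = 10 at most per participant.
- Number of sessions: General Overview gives 3 testing and 12 intervention visits, 15 in all. With testing at Visits 1, 7 and 15, 15 − 3 = 12 sessions remain. The intervention column header of the schedule leaves out Visit 8; this does not change the count.
- Whole study: 2 × 12 = 24 at most per participant.

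**Test days**
- The Assessment Schedule shows neither drink nor blood measurement at Visits 7 and 15. On that basis the risk is knowledge carried over from training sessions.
- One-Minute Anaerobic Threshold Test, however, requires β-HB immediately after that test. That reading comes too late to affect the same day's tests.
- Cycling Intervention also describes β-HB and the study drink one hour before exercise testing, and then speaks of training in the same paragraph. If this applies to test visits, a post-drink reading would directly precede the endurance test, in addition to the 10.
- These sections do not agree and must be reconciled. Exposure on test days may be higher than the schedule suggests.

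**Allocation wording**
- If the even or odd number is the study ID, anyone who knows the ID knows the arm.
- If it is a number drawn at random, the ID discloses nothing, but the text does not say so.
- Under either reading, no step is described that hides the next assignment from those who enrol.

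**The case against.** The strongest reply is that the plan takes blinding seriously. It separates the mixer, hides the drink, and commits the rest of the team to staying blinded. Rostering and access to values may be settled in working procedures outside these documents. The cadence rule for failure is objective, and the study is exploratory. All of this stands, and it limits what can be claimed about consequences. It does not close the gap: the commitment to stay blinded has no mechanism for β-HB, and the voluntary stop and the encouragement remain alongside the cadence rule.

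A reader might infer more than the text supports:
- **That the blind is broken.** The documents do not show that the same people take fingersticks and run endpoint tests. They only fail to require separation. They also give no β-HB values, so how well the arm could be guessed is unknown.
- **That the endurance result will be biased by some stated amount.** No such amount can be derived, and no bias is claimed for VO2.
- **That allocation is predictable alternation.** The sentence mentions a random number generator and can be read as a random draw whose parity sets the arm. A separate log of arms also fits that reading better. Ambiguity is all that can be asserted.

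It is also fair to say that β-HB is not the only cue. The Risks section lists poor or bitter taste as a more common side-effect of KE and names gastrointestinal symptoms. Controlling access to β-HB would leave those cues in place.

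**Conclusion.** The point holds as a gap in the protection of the declared double blind, and it should be fixed. Staff counted as blinded must take readings that are likely to indicate the arm, up to 10 per participant before the 5-session comparison and up to 24 over 12 sessions. Nothing keeps those values from the people who run and encourage a primary endurance test that can end by choice, or the anaerobic test. The omission can be read directly from the text. That it leads to bias is a possibility, which depends on the same staff doing both jobs and on β-HB differing visibly between arms. The counts assume the maximum of 3 samples per visit and, following the schedule, no drink on test days. The even/odd wording is a secondary matter of clarity and concealment.

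**What to change.** (a) State that post-drink β-HB values are not disclosed to participants, or to anyone who runs or encourages that participant's endurance and anaerobic tests, and that they are filed apart until unblinding. Existing staff who do not run that participant's endpoint tests take the fingersticks and pass on only the glucose result needed for the existing check. Masking the display is an alternative only if the shared glucose and β-HB device allows it, which the documents do not say. The drink mixer stays out of data collection, and no decision in the plan rests on β-HB, so no existing check is lost.

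(b) Replace the even/odd wording with a computer-generated 1:1 list held by the drink mixer, release each assignment only after enrolment, and use study IDs that carry no arm information.

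(c) Reconcile the Assessment Schedule, One-Minute Anaerobic Threshold Test and Cycling Intervention on whether drink and β-HB measurement occur at test visits.

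The cost is protocol wording, an allocation list, and minor rostering and filing work, with no added visits or samples. The change limits staff and participant inference from β-HB only; it does not deal with taste or side-effect cues.
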